Thus far, we treated 50 transplant recipients with third party donor derived CMVpp65-specific T-cells between 10/14/11 and 11/28/16, evaluable for response assessment as of 6/20/17. Patients had received an unmodified (N=11) T-cell depleted HCT (N=33) or cord blood (n=6), transplant. Fifteen were treated for overt CMV disease involving CNS (N=6), GI (N=10) and Lung (N=2) and 35 for CMV viremia persisting despite >2 weeks of induction therapy with 1-3 antiviral agents. Patients had received a median of 3 (1-6) prior antiviral treatments.

Third party CMVpp65-CTLs were selected from a bank of lines generated under GMP conditions from normal HCT donors who specifically consented to use of their T cells in patients other than their designated transplant recipient. Selection was made on the basis of HLA restriction by at least one HLA allele shared by the patient and HCT donor, and matching for  $\geq$  2/10 recipient alleles. If such a line was not available, a patient could be treated with a line matched at only one HLA allele as long

as the restriction was through that matched allele. Patients received 3 weekly infusions of approximately 1x10^6 CMVpp65-CTL/kg/infusion. Patients were sequentially evaluated for clinical and radiographic changes, quantifications of CMV DNA by PCR and IFN+ CMVpp65-specific T-cells in the blood. Responses were assessed 28-42 days after the first of each cycle of CMVpp65-CTLs. Response in patients with CMV disease was considered complete (CR) if all sites were cleared of virus by biopsy and blood sampling and partial (PR) if symptoms resolved and viremia met criteria of PR. In patients treated for persistent viremia, responses were complete if CMV DNA was cleared in repeated testing, and partial if the level of CMV fell based on the testing method by >50% (N=2) or by 2xLog10 (N=12).

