a The Safety in-person follow-up visit will overlap with the weekly follow-up visit during week 6 or 7. Evaluate CMV DNA weekly during both weeks. Perform assessment of CRS and ICANs per institutional standards to align with FACT requirements

b Evaluation may be completed by phone

c CBC & CMP

d For women of childbearing potential

e In addition, as available through medical records, high resolution HLA typing of the allograft donor for alloHCT recipients or low resolution HLA typing of the organ donor for SOT recipients

f Per section 8, not necessary if CT scan is done

g On each dosing day, monitor vital signs prior to the infusion, immediately after the infusion, and at 1, 2 and 4 hours ( $\pm$  10 minutes at each time point) following initiation of the infusion

h If patient is given additional cycles of ATA230, calendar will restart from Day 0. Doses are given weekly and can be held at the discretion of the PI or in the case of severe toxicity related to infusion

i Tests quantitating CMV viremia by CMV DNA copies per milliliter of blood should be obtained weekly for the first 8 weeks post-initial infusion with CMV-specific T-cells, and then at approximately monthly intervals until 6 months post infusion

j Any adverse events observed at screening, should be included as medical history

k GvHD evaluations to be performed at pretreatment, baseline (D1) and weekly (D7 and D14) for the first 3 infusions. Then week 5 (Day 28 – 32). For patients receiving more than 2 cycles: baseline at the start of each cycle.

l GvHD consensus to be performed on Day 30 from the first infusion and at 100 ( $\pm$  10) days post first CMV CTL infusion of last cycle

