## **12.0 CRITERIA FOR THERAPEUTIC RESPONSE/OUTCOME ASSESSMENT**

The primary endpoint of this study is to assess whether the infusion of adimleculeucel has therapeutic activity in curing CMV infections in recipients of HCT, SOT recipients, HIV, other immunocompromised states or immune competent subjects who require therapy. This study specifically will evaluate the therapeutic efficacy and persistence after infusion of adimleculeucel derived from third party donors for the treatment of CMV infections. The second clinical end point of this study is safety, especially the evaluation of GvHD induction after infusion of the third party adimleculeucel.

The responses of CMV infections will be clinically monitored as detailed under section 10. Responses to adoptively transferred T-cells are usually not observed until the T-cells have had time to expand within the transplant recipient, a period of at least 3 days, and as many as 18-21 days after the T-cell infusion. Final responses will be captured in CRDB and scored between days 28-42 post the final infusion of each cycle. Such window of evaluation ends the first day of the following cycle if patient switches cell lines and overlaps days 28-42. Best response observed in the full course of treatment will also be recorded as a distinct entity.

**Clinical responses** will be considered complete if all manifestations of CMV disease have resolved and/or the patient no longer has detectable CMV DNA by PCR.

**Partial response** will be defined as a  $2 \times \text{Log}_{10}$  reduction in the level of CMV DNA detected in the patients blood and/or improvement in clinical parameters of CMV infection such that the patient is symptom-free. For patients with a baseline CMV PCR  $< 13,800$  copies/mL a partial response will be defined as having a CMV PCR of  $< 137$  copies/mL on two occasions during the assessment period.

**Stable disease** will be defined as no change in the clinic severity of disease in any organ and CMV DNA is decreasing by the time of the evaluation time point but may be higher than the baseline CMV PCR (reflecting an increase that can occur during in vivo expansion of CMV-CTLs) and has not decreased by  $2 \times \text{Log}_{10}$ .

**Progressive disease** will be defined as disease progression by clinical and radiologic parameters, ascribable to CMV infection in any affected organ, will unchanged or increased levels of CMV DNA.

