### **14.0 BIOSTATISTICS**

A phase 2 trial design will be applied to determine the efficacy and safety of adimlecleucel for the treatment of marrow transplant patients with CMV. The endpoint of this study is complete response or partial response, as defined in Section 12. It is anticipated that accrual will be completed within 3 years.

The study design for HCT recipients aims to detect between response rates of 0.40 and 0.56 in the population. This two-stage design has a target sample size of 69 evaluable patients. If 15 or fewer patients respond in the first 36 patients that are evaluable for outcome assessment, then the trial will be stopped. If at least 16 patients respond, then 33 additional patients will be accrued for therapeutic response assessment. At the conclusion of the trial, if 32 or fewer patient responses are observed, we will conclude that the treatment is not sufficiently active. This design has a power of at least 0.90 for a population CR/PR rate equal to 0.56 using a one-sided test with type 1 error rate of 0.10. To reach 69 evaluable patients, it is anticipated that 81 patients will be recruited.

Based on the limited data in the setting of SOT recipients as well as immune deficient and immune competent individuals, results for these patients will be analyzed separately and will be descriptive.

In order to reduce patient risk, the study design includes early termination in the event of excessive graft versus host disease or solid organ rejection, requiring addition of immunosuppressant therapy to doses above those at the time of enrollment on trial, during the accrual period. The calculation is based on a group sequential design in a single-arm trial with a binary outcome.

Failure type	# of failures needed to stop the study	Failure rate in the population	Probability boundary is crossed
Acute GvHD (grades 3-4)  Or solid organ transplant rejection	3 within the first 15 patients	0.06	0.10
	4 within the first 24 patients  5 within the first 35 patients  6 within 51 patients	0.20	0.90

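### Section 12 asks for a second PCR only for the low-load partial response; the virologic CR and the 2-log PR have no stated confirmation

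*Combined protocol and SAP*

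**What the plan says.** Section 14.0 sets the endpoint: "The endpoint of this study is complete response or partial response, as defined in Section 12". It feeds a two-stage rule for HCT recipients: stop if 15 or fewer of the first 36 evaluable patients respond, and conclude insufficient activity if 32 or fewer of 69 respond.

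Section 12.0 gives three virologic routes to response:

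- **CR:** "all manifestations of CMV disease have resolved and/or the patient no longer has detectable CMV DNA by PCR".
- **PR, general:** a 2 × log10 "reduction in the level of CMV DNA detected in the patients blood and/or improvement in clinical parameters of CMV infection", the latter to the point of being free of symptoms.
- **PR, baseline below 13,800 copies/mL:** under 137 "copies/mL on two occasions during the assessment period".

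The first two state no number of readings, no repeat and no duration. No other section adds one.

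Final responses are "scored between days 28-42 post the final infusion of each cycle". Best response over the whole course is recorded as well, and Section 14.0 does not say which of the two is analysed.

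PCR is weekly through week 8. For the visit overlapping weeks 6 and 7, footnote a to the schedule table in Section 10.2.3 adds: "Evaluate CMV DNA weekly during both weeks".

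In the earlier 50-patient series described in Section 3.0, for patients treated for persistent viremia, "responses were complete if CMV DNA was cleared in repeated testing".

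**The concern.** The authors saw a need for repeat testing in one route and did not state it for the other two. One of those two is the best category. As worded, the better outcome can rest on less evidence than the lesser one, and the standard changes at 13,800 copies/mL without a stated reason. With several readings in the window and no rule on which one counts, two assessors could score the same patient differently.

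The count at stake is CR+PR, which decides whether the trial continues after 36 patients and whether the product is called active after 69. A transient undetectable value, or a transient 2-log fall, could enter that count.

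**Working it through.** **1. Reproduce the design.** Inputs from Section 14.0: n1 = 36, continue with at least 16 responses; n = 69, active with at least 33; null 0.40, alternative 0.56.

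P(declare active | p) = Σ over x = 16 to 36 of Bin(x; 36, p) × P(Y ≥ 33 − x), with Y ~ Bin(33, p).

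- p = 0.40: 0.0999 (stated 0.10)
- p = 0.56: 0.9001 (stated at least 0.90)

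The design figures are correct and are not in question.

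**2. Compare the two PR thresholds.** log10(13,800/137) = 2.003. The low-load cut-off is therefore the general 2-log fall written as an absolute value at the boundary. At a baseline of exactly 13,800 the general route applies: 13,800/100 = 138 copies/mL, with no repeat stated. Just below 13,800 the patient needs under 137, twice.

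**3. Compare categories within the low-load group.** The readings are invented and only the virologic route is considered.

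| Readings in the window (copies/mL) | Section 12.0 as worded |
|---|---|
| 90, 400, 400 | Not PR: below 137 only once |
| undetectable, 400, 400 | CR may be scored: no repeat stated |

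**4. Count the readings available.** With the third infusion on Day 14, the window runs from Day 14 + 28 = Day 42 to Day 14 + 42 = Day 56. Weekly PCRs at weeks 6, 7 and 8 give about three readings in a full window. If best response is the analysed quantity, more readings come into play.

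**5. Direction.** Anyone who meets a criterion on two readings also meets it on one. If any reading in the window may be scored, the unconfirmed count is never below the confirmed count.

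**6. Illustrate the size.** The documents give no rate of transient low readings, so this is assumption only. Let f be the share of true non-responders counted as responders, at a true rate of 0.40. The observed rate is 0.40 + 0.60f, put into the formula in step 1.

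| f | Observed rate | P(declare active) |
|---|---|---|
| 0 | 0.400 | 0.100 |
| 0.02 | 0.412 | 0.140 |
| 0.05 | 0.430 | 0.217 |
| 0.10 | 0.460 | 0.384 |

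**The case against.** **Silence is not a rule of one.** A reader might infer that CR needs only one undetectable PCR and that any isolated low reading makes a responder. Section 12.0 does not say that. Its CR wording describes a state, and a patient reading undetectable, 400, 400 has detectable DNA when the window closes. The stable-disease definition refers to an evaluation time point, which suggests one scoring moment rather than the best of three. A single low but detectable value does not count in the low-load group, and from 13,800 upwards a 100-fold fall is needed. This stands: the finding is that confirmation is not specified.

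**The second reading may be deliberate in the low-load route.** For baselines well below 13,800, a value under 137 can be less than a 2-log fall: from 1,000 it is log10(1,000/137) = 0.86. That could justify more evidence there. It does not explain why the better category, in the same patients, has no stated repeat.

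**Larger error rates are not supported.** A reader might assume that 20% of tests are transiently negative and obtain 1 − 0.8³ = 0.49 for at least one negative in three. That needs an assumed test rate, independent serial PCRs and a rule that any negative counts. Likewise, an observed rate of 0.45 gives 0.324, but five points of all patients is 0.05/0.60 = 8.3% of non-responders, a share found nowhere in the documents.

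**The null may already absorb it.** Section 14.0 gives no basis for 0.40. If that rate was set under the same unconfirmed definition, the inflation in step 6 does not apply in full.

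**Comparability with the earlier series.** A reader might infer that this wording breaks the comparison with the 64% response rate. No such comparison is planned. The series already differed: its assessment was timed from the first infusion of a cycle, its CR for disease needed biopsy clearance, and two of its PRs rested on a fall of more than 50%. It shows only that repeated testing was once part of CR for viremia.

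**Not every window holds three PCRs.** Cycles last 35 days (Section 9.1), and Section 12.0 closes the window when a cell-line switch starts a new cycle. A switch at Day 35 leaves no reading in Days 42–56. Section 10.0 also allows assessments to be held. This stands and bears on the fix.

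**Conclusion.** The point holds as an unspecified and uneven confirmation standard in the primary endpoint. The two-occasion requirement covers one virologic route of three. The same 2-log fall needs two readings just below 13,800 copies/mL and has no stated repeat at or above it. In low-load patients, the wording allows CR on one undetectable value while refusing PR on one low detectable value.

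The effect runs towards more responders if any reading in the window may be scored. Its size cannot be found from the documents. The range 0.14 to 0.38 against 0.10 is illustrative: it assumes that 2% to 10% of true non-responders are miscounted and that 0.40 is the rate under a confirmed definition. It shows that a small misclassification would matter to the decision, not that this much occurs.

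This should be corrected. It does not invalidate the design. The clinical alternatives in the CR and PR definitions are a separate matter and are unaffected.

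**What to change.** In Section 12.0:

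1. Extend the existing two-occasion requirement within the assessment period to the virologic CR and to the 2-log PR.
2. Score an unconfirmed value in the next lower category that is met.
3. State how a window with only one PCR, or none, is scored, whether through a missed test or closure by a cell-line switch.

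This uses the protocol's own standard. Requiring two consecutive readings with no later failure would exceed it and could leave shortened windows unscorable.

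Cost: in a full window the scheduled weekly PCRs already supply the second sample, so no visit is added and the sample size stays the same. The CR/PR rate will be slightly lower, and some patients with a single PCR will fall to a lower category. The sponsor should confirm that 0.40 and 0.56 are still the intended rates under the confirmed definition. Because the action table in Section 9.1 keys further cycles to the response category, the sponsor should also say whether the confirmed category is for endpoint scoring only.

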## **4.2 Intervention**

The T-cells to be infused will be selected based on criteria mentioned in section 4.0 from our bank of GMP grade adimleculecel. T-cells will be administered by bolus intravenous infusion. In this phase II trial, patients will be treated at doses of  $1 \times 10^6$  adimleculecel /kg/dose/week (with an acceptable range of  $0.8 - 1.2 \times 10^6$  cells/kg) for 3 weeks or total dosing of  $2.4 - 3.6 \times 10^6$  cell/kg per cycle. Patients

will be observed for the following 3 weeks. Additional 3 week courses of adimlecleucel may be administered if levels of CMV DNA in blood are still detectable despite disease stabilization or improvement.

The rationale for the doses of T-cells proposed for treatment stems not only from our Phase I trial but also from our studies quantitating doses of unselected T-cells required to induce GvHD and the doses of EBV-CTLs required to induce regressions of EBV lymphomas following allogeneic HCT. Our studies of the incidence of GvHD in recipients of T-cell depleted matched or 1 allele mismatched HCT suggest that a dose of  $\geq 10^5$  allo cytotoxic T-cell (CTLp)/kg, as quantitated by limiting dilution analyses, represents the threshold dose for development of grade II or greater GvHD (44). In-vitro sensitization of T-cells against CMV or EBV for a period of 28 days results in preferential proliferation of antigen specific T-cells with simultaneous depletion of alloreactive T-cells by at least 100 fold (45). Therefore, in the doses of adimlecleucel proposed for treatment in this trial ( $1 \times 10^6$ /kg x 3 T-cells /kg), the doses of potentially alloreactive T-cells administered would be estimated to be below the GvHD threshold. In practice, the CMVpp65CTL after this culture period do not contain detectable allocytotoxic activity against patient or fully allogeneic PHA blasts. Indeed, this lack of alloreactivity is a release criterion that must be met to use the cells for treatment.

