### 9.1 Treatment with adimleculecel

This study will enroll subjects regardless of the underlying susceptibility to CMV, including alloHCT, SOT, human immunodeficiency virus, other immunocompromised states, and immune competent subjects who require therapy. Subjects must have active CMV viremia or disease for  $\geq 2$  weeks

despite treatment with antiviral therapy or must be intolerant to antiviral therapy due to treatment-related toxicity or comorbidities such as renal insufficiency or myelosuppression.

Subjects will receive adimleculeucel from cell lines generated from normal alloHCT donors or healthy donors, specifically consented for this purpose, based on having a partial match of  $\geq 2$  HLA alleles shared between the donor and the subject including the HLA restricting allele of the adimleculeucel cell product.

Adimleculeucel will be administered in cycles lasting 5 weeks (35 days). During each cycle, subjects will receive IV adimleculeucel at a dose of  $1 \times 10^6$  cells/kg (with an acceptable range of 0.8 –  $1.2 \times 10^6$  cells/kg) for 3 weeks or total dosing of  $2.4 - 3.6 \times 10^6$  cells/kg per cycle on days 0, 7, and 14. Tests quantitating CMV viremia by CMV DNA copies per milliliter of blood should be obtained weekly for the first 8 weeks post-initial infusion with CMV-specific T-cells, and then at approximately monthly intervals until 6 months post infusion.

Additional 3 week courses of adimleculeucel may be administered if patients have ongoing disease and/or levels of CMV DNA in blood are still detectable. These secondary courses will usually employ T-cells from the same third party donor. However, adimleculeucel derived from an alternate third party donor's CMV pp65-specific T-cells may be used if no further cells from the same donor are available or for patients with stable or progressive CMV infection refractory to antiviral drugs, since infusion of virus specific T-cells from a secondary donor specific for a different CMV peptide and restricted by the same or an alternate HLA allele shared by the recipient has, in several cases, induced durable regression of disease (23).

Subjects will generally be treated for a maximum of 2 cycles, though subjects achieving PR by the end of Cycle 2 may receive a third cycle. Subjects with PD at the end of Cycle 1 or later, or who experience unacceptable toxicity, will be offered Switch Therapy if appropriate.

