## 10.2 Follow-up

### 10.2.1 Monitoring during the first 8 weeks

Patient will be monitored for eight weeks after administration of the first dose of adimleculeucel. During this period, perform the following:

- Assessment of SAEs and concomitant medications
- Assessment of CRS and ICANs per institutional standards
- CMV DNA quantitation by PCR to determine if an additional cycle is needed
- Assessment/Phone assessment for symptoms of GvHD weekly at baseline and prior to each infusion, week 5 (Day 28 – 32) if patient not receiving subsequent cycles of CMV-CTLs
- The timing of Consensus GvHD assessments is dependent on the number of infusions patients receive and will be performed as per institutional standards.

For patients who receive subsequent cycles of cells, the monitoring calendar will re-start with the first dose of the subsequent cycle, with the exception of GvHD assessments, which will occur as above.

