Patients lost to followup either during therapy or followup or patients with changes in antiviral therapy during treatment with adimleculeucel such that any changes in the extent of CMV viremia or disease cannot be attributed to cellular therapy will be defined as not evaluable for outcome assessment. Patients evaluable for some but not all cycles of cellular therapy will be evaluated as such.

Graft versus Host Disease initially developing 10 to 100 days post T-cell infusion will be considered to be potentially ascribable to the T-cell infusion. Graft versus Host Disease will be diagnosed and clinically graded using the standard criteria of the IBMTR/NMDP Consensus Panel. Whenever,

possible, the diagnosis will be confirmed by biopsy of skin or other involved organ, using the pathological criteria of Woodruff et al. Patients with preexisting GvHD of grade 1 severity not requiring systemic steroids, or patients with a prior history of GvHD who have resolved this process sufficiently so that they no longer require parenteral steroid treatment will be considered to have developed an exacerbation or worsening of GvHD ascribable to the T-cell infusion if they redevelop clinical evidence of grade 2 or greater GvHD 7 to 100 days after a dose of T-cells.

For the evaluation of toxicities, the NCI Standard Toxicity Scale 4.0 will be employed.

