### **13.0 CRITERIA FOR REMOVAL FROM STUDY**

In accordance with the Declaration of Helsinki, ICH Good Clinical Practice Guidelines, and the US FDA Regulations, a patient has the right to withdraw from the study at any time for any reason without prejudice to his/her future medical care by the physician or at the institution. The Investigator also has the right to withdraw patients from the study (see below). Should a patient (or a patient's legally authorized representative) decide to withdraw, all efforts will be made to complete and report the observations as thoroughly as possible.

A complete final evaluation should be made at the time of the patient's withdrawal, the Study Status Outcome form in the case report form should be completed with an explanation of why the patient is withdrawing, and an attempt should be made to perform a follow-up evaluation.

Patients may be removed from study if one or more of the following events occur:

- Withdrawal of consent by subject
- Occurrence of an AE that precludes further participation
- Subject chooses to take a prohibited treatment, such as use of a different investigational medication or device
- Refusal of the patient to continue treatment observations
- Significant noncompliance on the part of the patient
- Development of another disease (e.g. Adenovirus infection) that requires therapeutic intervention that would interfere with the interpretation of results from the study
- Decision by the Investigator that termination is in the patient's best medical interest
- Lost to follow-up

Patients who received a concomitant antiviral therapy due to toxicity of the current therapy or occurrence of another viral infection will be replaced. Data regarding safety of the CTLs will still be collected for those patients.

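### The rule on antiviral changes stops at the end of treatment, but response is scored 28-42 days after the last infusion, so a patient rescued by a CMV drug in between can score CR or PR

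*Combined protocol and SAP*

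**What the plan says.** Section 12 (therapeutic response/outcome assessment) defines who is not evaluable. One sentence names two groups: those lost to follow-up "either during therapy or followup or patients with changes in antiviral therapy during treatment with adimleculeucel". For the second group the sentence continues "such that any changes in the extent of CMV viremia or disease cannot be attributed to cellular therapy will be defined as not evaluable". The first group is covered in therapy and in follow-up, the second only in treatment. The protocol does not define treatment for this purpose.

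Section 12 also fixes the time of scoring: "Final responses will be captured in CRDB and scored between days 28-42 post the final infusion of each cycle". Section 9.1 puts the infusions on days 0, 7 and 14 of a 35-day cycle. Section 4.2 says that after dosing patients "will be observed for the following 3 weeks", and Section 10.2, headed as follow-up, opens with 10.2.1, "Monitoring during the first 8 weeks".

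The CR and PR definitions in Section 12 set no condition on new or increased antivirals. Section 13 adds one replacement rule: "Patients who received a concomitant antiviral therapy due to toxicity of the current therapy or occurrence of another viral infection will be replaced". It does not name a drug given because CMV itself failed to respond.

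Section 14 takes CR or PR as defined in Section 12 as the endpoint and tests it in evaluable HCT recipients. The trial continues with at least 16 responders in 36, and the product is called sufficiently active with at least 33 in 69.

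**The concern.** The interval in which an antiviral change matters ends before the response is measured. Suppose a patient's CMV does not respond to the cells, a CMV-active drug is started or increased after treatment ends, and CMV DNA is undetectable at scoring. Nothing in the text takes that patient out of the evaluable set, and nothing in the CR or PR definitions withholds the response.

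The trial has one arm, so no control group absorbs the effect of such drugs. Patients who fail the cells are the likeliest to be given another CMV drug before scoring. Counting their clearance as a cell response can only raise the observed rate, and that rate is the trial's only formal efficacy test.

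**Working it through.** **Timing.** The last infusion is on day 14 (Section 9.1) and scoring is 28-42 days later (Section 12), so scoring falls on day 14 + 28 = 42 to day 14 + 42 = 56.

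| Reading of treatment | Uncovered days | Share of time from first infusion to scoring |
|---|---|---|
| Infusions, to day 14 | 28 to 42 | 28/42 = 67% to 42/56 = 75% |
| Whole cycle, to day 35 | 7 to 21 | 7/42 = 17% to 21/56 = 37.5% |

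On both readings the scoring window itself lies outside treatment. When another cycle follows, its own treatment period covers part of the window. If the patient switches cell lines, Section 12 also ends the window on the first day of the new cycle. The exposure is therefore mainly in the last cycle.

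**The plan's own figures.** From Section 14: continue if X1 ≥ 16 of 36, active if X1 + X2 ≥ 33 of 69.

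P(active | p) = sum over x = 16 to 36 of P(X1 = x) × P(X2 ≥ 33 − x), with X1 ~ Bin(36, p) and X2 ~ Bin(33, p).

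This gives 0.0999 at p = 0.40 and 0.9001 at p = 0.56. The stated type 1 error of 0.10 and power of at least 0.90 are reproduced.

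**Effect of the gap.** Let f be the share of cell failures who start or increase a CMV drug in the gap, meet CR or PR at scoring and are counted. The documents do not give f, so it is an assumption. At a true cell response of 0.40, the observed rate is 0.40 + 0.60f.

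| f | Observed rate | P(active) | Expected false responders in 69 (69 × 0.60 × f) |
|---|---|---|---|
| 0 | 0.400 | 0.0999 | 0 |
| 1% | 0.406 | 0.119 | 0.4 |
| 2% | 0.412 | 0.140 | 0.8 |
| 5% | 0.430 | 0.217 | 2.1 |
| 10% | 0.460 | 0.384 | 4.1 |

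**If those patients become not evaluable instead.** They leave the denominator and are replaced, so the rate among evaluable patients is 0.40 / (0.40 + 0.60(1 − f)). At f = 5% this is 0.412 and P(active) is 0.141. At f = 10% it is 0.426 and P(active) is 0.196. Extending the exclusion reduces the bias but does not remove it. Scoring them as non-responders leaves the rate at 0.40 and P(active) at 0.0999.

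**The case against.** The best reply is that treatment is undefined and can be read broadly. Section 12 speaks of the best response over the full course of treatment, which could be taken to include the scoring window. Section 10.2.1 counts its eight weeks from the first dose, so the follow-up heading overlaps dosing and is not a clean contrast. The stated purpose of the exclusion is attribution, and an investigator might apply it to a rescue drug at any time before scoring. This stands in part: the protocol nowhere says that a rescued patient counts as a responder. A reader might infer that it does, or that most of the time to scoring is unprotected. The first is only the literal result of the wording, and the second holds only if treatment means the infusions alone. But the same sentence names follow-up for one group and omits it for the other, and evaluability in a single-arm trial should not rest on an unwritten reading.

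The second reply is that f may be small. Eligible patients have CMV that persists or progresses on antivirals, carries a resistance mutation, or cannot be treated further because of drug toxicity. Section 3 reports a median of 3 prior antiviral treatments in the earlier cohort. High rescue rates are not obvious in such patients. This stands, and it is why small values of f belong in the table.

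The third reply concerns the remedy. A reader might infer that every CMV-driven drug change from day 0 should count as non-response. The documents do not support going that far. The plan already makes non-attributable changes during treatment not evaluable, and Section 12 notes that CMV DNA can rise while the cells expand. If 5% of true responders were reclassified in this way, the rate would fall from 0.56 to 0.56 × 0.95 = 0.532 and power from 0.90 to 0.80.

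**Conclusion.** The gap is real on either reading of treatment, and it lies mainly in the last cycle. Neither the CR and PR definitions nor the replacement rule in Section 13 closes it. Section 13 also allows removal for a prohibited treatment, but that is optional and its example is an investigational product. The direction of bias is known; the size is not. Any f above zero raises the chance of a false conclusion of activity, from 0.119 at f = 1% to 0.384 at f = 10%. These figures assume a true cell response of 0.40 and that every rescued failure in f is scored as a response.

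This is not an error in the sample size, whose figures reproduce, and it is not evidence that any response has been misclassified. It is a scoring rule that should be completed before the decision rule is applied.

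**What to change.** In Section 12, change the interval for antiviral changes so that it runs from the first infusion of the cycle until that cycle's response is scored. The existing attribution condition and the not-evaluable outcome stay as they are.

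Add one sensitivity analysis. Report the CR/PR rate and the 33/69 decision again, with patients who start or increase a CMV-active drug for CMV after the last infusion and before scoring counted as non-responders. State which 69 patients enter it, for example the first 69 HCT recipients who are evaluable or are not evaluable for this reason alone.

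The cost is a sentence and one extra analysis. The Section 10 schedule already records concomitant medications through month 3, past the scoring window, so no visits are added. There may be a few more non-evaluable patients than the 81 − 69 = 12 allowed for, and the response rate may be slightly lower. The change affects scoring only, not care.
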